## 7.2 Adverse Events

AEs will be collected from the day the patient gives informed consent until 30 days after the final dose of study drug or until resolution of all serious adverse events (SAEs). Only those AEs that emerge or worsen after the date of first dose of randomly assigned study medication, i.e. treatment emergent adverse events (TEAE), will be reported. Adverse events with a missing start date will also be classified as TEAE.

Summaries of TEAE will include the number of patients with at least one TEAE for each treatment arm. When reporting by system organ class (SOC) and preferred term (PT), the reports will present the SOC in alphabetical order; while PTs within the SOC will be presented in order of overall decreasing frequency of occurrence in the combined baricitinib arms. A patient with multiple TEAEs (different PTs) coded to the same SOC will be counted only once for that SOC, but will be counted each time for different PTs within that SOC. A patient with separate events of the same PT (different start/stop dates) will be counted only once in the frequency tables for that PT.

TEAEs will be reported using the treatment that the patient received.

No statistical testing will be performed for comparisons of TEAEs.

An overview of all TEAEs will also be provided by treatment group using the types of AEs defined in the following subsections.

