#### ***7.2.7 Adverse Events of Special Interest***

Adverse events or laboratory results of special interest include infections; myelosuppressive events of anaemia (haemoglobin decreased), leukopenia (white blood cell count decreased), neutropenia (neutrophil count decreased), lymphopenia (lymphocyte count decreased), thrombocytopenia (red blood cell count decreased), thrombocythaemia (platelet count increased); hyperlipidaemia (lipids increased); hypercholesterolemia (cholesterol increased); and elevations in hypertransaminasaemia (aminotransferase increased) and hyperbilirubinemia (bilirubin increased). All TEAE for which the PT contains any of the above terms or that belong to the SOC 'Infections and infestations' will be considered an AE of special interest. The TEAE of special interest will be summarized for each treatment arm by SOC and PT and by decreasing frequency in the combined baricitinib arms.

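### SAP 7.2.7 defines ten non-infection conditions of special interest but plans no adverse event table that counts patients with each one

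*SAP*

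**What the plan says.** Section 7.2.7 lists infections and ten other conditions: anaemia, leukopenia, neutropenia, lymphopenia, thrombocytopenia, thrombocythaemia, hyperlipidaemia, hypercholesterolaemia, raised transaminases and raised bilirubin. Each of the ten is followed by a laboratory-style equivalent in brackets, as in "myelosuppressive events of anaemia (haemoglobin decreased), leukopenia (white blood cell count decreased), neutropenia (neutrophil count decreased), lymphopenia (lymphocyte count decreased". Infections has no bracketed partner.

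One selection rule covers them all: "All TEAE for which the PT contains any of the above terms or that belong to the SOC 'Infections and infestations' will be considered" of special interest. The output rule is "The TEAE of special interest will be summarized for each treatment arm by SOC and PT", with a second ordering by falling frequency across the two baricitinib arms.

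Section 7.2 fixes the counting. A patient with several PTs in one SOC "will be counted only once for that SOC, but will be counted each time for different PTs within that SOC". A patient with repeated events of one PT "will be counted only once in the frequency tables for that PT". The same section adds a summary: "An overview of all TEAEs will also be provided by treatment group using the types of AEs defined in the following subsections". Special interest is one of those types.

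**The concern.** By pairing the wordings, the SAP treats a clinical term and its laboratory-style partner as one condition for selection. It does not do so for counting. Once selected, the two wordings are separate PTs on separate rows, and no row for the condition brings them together.

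The section exists to show whether the named blood, lipid and liver events are more frequent on baricitinib. Section 7.2 rules out statistical testing of TEAEs, so the displayed counts are all the reader has. The active arms have about 36 patients each, and splitting a handful of cases over two rows can make a difference between arms hard to see.

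**Working it through.** **No plan figure to reproduce.** The SAP gives no expected rates for events of special interest. The structural part follows from the text alone; the numerical part rests on declared assumptions.

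**Step 1: which counts are available.**

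| Level | Duplicates removed? | Count for one condition? |
|---|---|---|
| PT row | within that PT | no, only one wording |
| SOC row | within that SOC | no, covers every selected PT in the SOC |
| Special-interest line in the overview | across all selected PTs | no, all ten conditions plus infections |
| Condition | not specified | not planned |

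Infections is the exception. It is defined as a whole SOC, so its SOC row is already a unique-patient count.

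**Step 2: PT rows cannot be added.** Suppose 3 of 36 patients have the clinical PT and 3 of 36 the laboratory-style PT. If they are the same patients, the condition count is 3 (3/36 = 8.3%). If they are all different, it is 6 (6/36 = 16.7%). The specified table looks the same in both cases.

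**Step 3: what the split can cost (illustration).** Arm sizes from section 1.3: 120 patients at 4:3:3 give 48, 36 and 36. Assume that each affected patient is reported under one wording only and that true incidence is p in an arm of 36. The threshold of 4 patients is for illustration and is not an SAP criterion.

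- Condition row: P(X ≥ 4), with X ~ Binomial(36, p).
- Either PT row: 1 − P(X₁ ≤ 3 and X₂ ≤ 3), with (X₁, X₂) multinomial with probabilities sp and (1 − s)p, where s is the share reported under the commoner wording.

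| p | Condition row | s = 50% | s = 80% | s = 90% |
|---|---|---|---|---|
| 8% | 32% | 11% | 20% | 26% |
| 12% | 64% | 31% | 47% | 56% |
| 16% | 85% | 56% | 70% | 78% |

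An even split is the worst case, and the loss shrinks as one wording dominates.

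**Step 4: dilution in the overview line (illustration).** Assume one condition at 12% on active and 2% on placebo (ratio 6), with infections at the same rate q in both arms, independent of the condition, and no other special-interest events. The pooled proportions are 1 − (1 − q)(0.88) and 1 − (1 − q)(0.98).

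| q | Active | Placebo | Ratio |
|---|---|---|---|
| 5% | 16.4% | 6.9% | 2.4 |
| 10% | 20.8% | 11.8% | 1.8 |
| 20% | 29.6% | 21.6% | 1.4 |
| 30% | 38.4% | 31.4% | 1.2 |
| 40% | 47.2% | 41.2% | 1.1 |

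Infections need not dominate that line. The share of its patients who have an infection is q / [1 − (1 − q)(1 − r)], where r is the rate of all other special-interest events. With q = 40% and r = 2% this is 0.40/0.412 = 97%. With q = 5% and r = 20% it is 0.05/0.24 = 21%.

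**Step 5: what the laboratory sections add.** Section 7.3.1 gives values and changes at each time point. Section 7.3.2 gives low/normal/high shifts for each parameter, but from baseline only to Week 16 and to the last observation; shifts to other visits are optional. Counts of patients with any post-baseline value beyond a threshold are planned only for ALT, AST, ALP and total bilirubin. Under section 7.3, unscheduled results go to listings, except where they supply the last value for a patient with no Week 16 measurement. A cytopenia that appears at Week 8 and resolves by Week 16 would therefore not show in the planned shift tables.

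**The case against.** The strongest reply is that all ten conditions are defined by laboratory values, and section 7.3 analyses those values by parameter and arm, whatever wording an investigator chose. This stands in part. The liver conditions are reasonably served by the threshold counts. Haematology and lipids have no such counts, and none of these tables counts reported TEAEs.

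A second reply is that section 1.1 leaves table formats to a companion document and lets formats change without an SAP amendment. Grouping rows may exist there; it is not available to check. However, which PTs form a condition, and that a patient counts once across them, is an analysis definition rather than a layout, and section 7.2.7 states a different presentation.

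A third is that this is a small phase 2 trial with descriptive safety reporting, where tables by SOC and PT are a legitimate choice. They contradict nothing in the SAP, so the point concerns a better method and not an internal error.

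Two stronger readings are tempting, and the text does not support them. A reader might infer that every listed condition lacks its own count; infections has one. A reader might also infer that infections hide the other events throughout. In the table by SOC, infections sit under their own heading, so dilution affects only the pooled line, and its degree depends on rates the SAP does not state.

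**Conclusion.** The point holds for the ten paired conditions. As written, no adverse event table gives unique patients per arm for any of them, PT rows cannot be summed, and the only pooled figure combines them with all infections. This follows from sections 7.2 and 7.2.7 without any assumed rate.

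The size is uncertain. At 12% incidence in 36 patients, a condition row reaches 4 or more patients with probability 64%, against 31% to 56% for either PT row. These figures assume one wording per patient and splits between 50/50 and 90/10. A true ratio of 6 would read as 2.4 down to 1.1 in the overview line for infection rates of 5% to 40%. It would be wrong to conclude that a safety signal will be missed: the laboratory tables give partial cover, and the PT rows remain visible. The primary analysis is unaffected.

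**What to change.** In section 7.2.7:

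1. Correct the thrombocytopenia pairing first. Its bracketed term refers to a decrease in red blood cells, not platelets; grouping on the text as it stands would count red-cell decreases as thrombocytopenia.
2. Define each of the ten non-infection conditions as a named group of PTs.
3. For each group and arm, report the number and percentage of patients with at least one event, counting each patient once across all PTs and SOCs in the group. Show the SOC and PT rows within the group.
4. In the section 7.2 overview, give infections and each group its own line.

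The cost is SAP wording, one grouping variable in the adverse event dataset and one extra table. No new data are needed.

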### **7.3 Clinical Laboratory Results**

Blood samples for hematology and serum chemistry and urine samples for urinalysis will be collected at baseline and Weeks 4, 8, 12, and 16 post-randomization. Blood samples for fasting lipid profiles will be collected at baseline and Week 16 post-randomization, and blood samples for immunoglobulins will be collected at baseline and Weeks 8 and 16 post-randomization. If a

patient decides to discontinue early from the study, samples for each of the parameters will be collected prior to discontinuation.

Analyses of laboratory values will be produced using the measurements collected the scheduled time points. The unscheduled assessments will only appear in data listings. An exception will be made for the analyses of the last measured values which for patients who do not have a measurement at Week 16 will be derived using the last collected scheduled or unscheduled measurement.

### ***7.3.1 Descriptive Statistics over Time***

At each of the post-baseline visits the change and percent change from baseline for each every quantitative clinical laboratory parameter will be derived. Descriptive statistics for the value and changes from baseline will be tabulated for each time point for each treatment arm.

### ***7.3.2 Shift tables and Categorical variables***

The grading of each laboratory parameter as low, normal or high will be compared from baseline to Week 16 and to the last observation, which should be the Week 16 or early termination visit. Shift tables will present the number and percent of patients who started in a category (low, normal, high) at baseline and category at the end of the study. Similarly, shift tables for the categorical urinalysis parameter will also be produced.

Shift tables comparing baseline to the other time points in the study may be generated if warranted after data review.

Additional shift tables will be constructed for the liver parameters – alanine aminotransferase (ALT), aspartate aminotransferase (AST), alkaline phosphatase (ALP), and total bilirubin (TBili). For each of the transaminases the number of patients with any post-baseline elevation exceeding 3 times the upper limit of the normal range (3xULN) will be counted by treatment arm. The counts of patients will be reported using subsets defined by the patients' baseline transaminase values; i.e.  $ALT \leq 1xULN$ ,  $1xULN < ALT \leq 2xULN$ . The analyses of ALT and AST elevations will also be performed using 5xULN and 10xULN. For TBili the number of patients with any post-baseline elevation exceeding 2xULN will be counted by treatment arm using the subsets  $TBili \leq 1xULN$  and  $TBili > 1xULN$ . For ALP the number of patients with any post-baseline elevation exceeding 1.5xULN (also 2xULN and 3xULN) will be counted by treatment arm.

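### No committed table counts patients with blood-count abnormalities that resolve before Week 16, and the last observation is defined inconsistently

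*SAP*

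**What the plan says.** Section 7.2.7 sets the scope. "Adverse events or laboratory results of special interest include infections; myelosuppressive events of anaemia", and the list continues with leukopenia, neutropenia, lymphopenia, thrombocytopenia and thrombocythaemia, among others. Although the list covers laboratory results as well as events, the rule that follows selects only treatment-emergent adverse events (TEAEs), by preferred term or by the infections system organ class.

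Section 7.3 gives the sampling. Its sentence on haematology, chemistry and urinalysis ends: "urine samples for urinalysis will be collected at baseline and Weeks 4, 8, 12, and 16 post-randomization". On extra samples it says "The unscheduled assessments will only appear in data listings", with one exception. The last measured value "for patients who do not have a measurement at Week 16 will be derived using the last collected scheduled or unscheduled measurement".

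Section 7.3.2 gives the categorical analysis: "The grading of each laboratory parameter as low, normal or high will be compared from baseline to Week 16 and to the last observation", the latter being one "which should be the Week 16 or early termination visit". On the remaining visits: "Shift tables comparing baseline to the other time points in the study may be generated if warranted after data review". For the liver tests it takes a different approach. For each transaminase it counts "the number of patients with any post-baseline elevation exceeding 3 times the upper limit of the normal range", with similar counts at higher multiples and for bilirubin and alkaline phosphatase.

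Section 7.3.1 adds descriptive statistics by visit and arm for every quantitative parameter. Under section 2.8 these generally include the minimum and maximum.

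**The concern.** The SAP singles out blood counts as a safety interest and samples them four times after baseline, but it commits to classifying them only at the end. A count that falls at Week 4, 8 or 12 and recovers by Week 16 is shown as normal at the end in both committed shift tables. The liver tests do not have this gap, and section 7.4 tabulates threshold abnormalities in blood pressure and pulse at each time point. So the SAP applies a suitable approach elsewhere but not to the blood counts it names.

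The second issue is the meaning of last observation. Section 7.3 lets an unscheduled sample fill that role when Week 16 is missing and sets no on-treatment limit. Section 7.3.2 expects the Week 16 or early termination visit. Two programmers could build different tables from these sentences. Under the section 7.3 reading, a normal sample taken after treatment stopped can replace a low value seen on treatment.

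What is at stake is the reported number of patients per arm with a low or high blood count on treatment. The primary efficacy result is not affected.

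**Working it through.** The SAP states no cytopenia rate, so there is no figure to reproduce. The check has two parts.

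**1. Following patients through the rules** (all normal at baseline)

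| Course | Week 16 shift table | Last-observation shift table |
|---|---|---|
| Low at Week 8, normal at Weeks 12 and 16 | normal | normal |
| Low at Weeks 4 to 16 | low | low |
| Low on an unscheduled on-treatment sample, normal at scheduled visits | normal | normal |
| Low at Week 4, stops, no Week 16 value, later unscheduled recheck normal | no value | normal under 7.3; the early termination result under 7.3.2 |
| As above, but recheck still low | no value | low under 7.3; the early termination result under 7.3.2 |

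The low values in rows 1 and 3 reach no committed categorical table, nor does the one in row 4 under the section 7.3 reading. They may appear elsewhere: in a listing, as a by-visit minimum (scheduled samples only, and only if lowest in the arm), or as a TEAE if reported with a matching term.

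**2. Scale, for illustration only**

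Inputs: four scheduled visits (section 7.3). Arm size is 120 × 3/10 = 36 per baricitinib arm (section 1.3). Two quantities are assumed: a, the chance of a low value at a visit for a patient not low at the previous one, and s, the chance that a low patient is still low at the next visit. All patients are taken to reach Week 16.

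- P(ever low) = 1 − (1 − a)^4
- P(low at visit v): L_v = a(1 − L_{v−1}) + s·L_{v−1}, with L_0 = 0
- Missed share = 1 − L_4 / P(ever low)

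For a = 0.05, P(ever low) = 1 − 0.95^4 = 0.185, or 36 × 0.185 = 6.7 patients per arm. With s = 0.5: L_1 = 0.05; L_2 = 0.0475 + 0.025 = 0.0725; L_3 = 0.0464 + 0.0363 = 0.0826; L_4 = 0.0459 + 0.0413 = 0.087. Missed share = 1 − 0.087/0.185 = 53%.

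| s (a = 0.05) | Low at Week 16 | Patients shown, of 6.7 ever low | Missed share |
|---|---|---|---|
| 0 | 4.8% | 1.7 | 74% |
| 0.05 (chance level) | 5.0% | 1.8 | 73% |
| 0.25 | 6.2% | 2.2 | 66% |
| 0.5 | 8.7% | 3.1 | 53% |
| 0.75 | 12.7% | 4.6 | 32% |
| 1 | 18.5% | 6.7 | 0% |

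The missed share depends little on a. At s = 0 it is 75% for a = 0.02 and 74% for a = 0.10; at s = 0.75 it is 32% for both; at s = 1 it is 0%.

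A second model, with equally correlated normal values at the four visits, gives results inside this range. At 5% low per visit, 12.0% (correlation 0.7) to 18.5% (correlation 0) are ever low, so 1 − 5/12.0 = 58% to 1 − 5/18.5 = 73% are missed. At 10% per visit, 21.7% to 34.4% are ever low, so 54% to 71% are missed. At correlation 0.9 the missed shares are 43% and 39%.

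**The case against.** The strongest reply is that the information is not lost. All four scheduled samples are used in section 7.3.1, and the by-visit minimum shows the deepest value in each arm. A patient withdrawn for a low count that was reported as an adverse event appears under section 7.2.5, by severity under 7.2.6 and, if the term matches, under 7.2.7. By-visit shift tables are foreseen, and section 1.1 allows extra analyses without amendment. This is a phase 2 trial of about 120 patients. All of that stands and limits the consequence. It does not supply the missing number: a minimum is one value and not a count of patients, adverse event tables depend on reporting and coding, and a table decided after data review is not a pre-specified safeguard.

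Some stronger readings are not supported:

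- A reader might infer that cytopenias in general disappear from the tables. Only those that resolve do; persistent ones are counted.
- A reader might infer that any low value followed by a recheck is hidden. That needs both a missing Week 16 value and a normal recheck. Section 7.3 also calls for samples before early discontinuation, and how long rechecks continue is not stated in the SAP.
- A reader might infer a bias toward no difference between drug and placebo. That would need recovery or stopping to differ between arms in a particular way, and the SAP has no figures on this.
- A reader might extend the point to lipids. They are scheduled only at baseline and Week 16, so a worst scheduled value is the Week 16 value.

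**Conclusion.** The point holds for the analyses the SAP commits to. Named haematology abnormalities at Weeks 4, 8 or 12 that resolve by the end enter no committed categorical table, and no other committed output gives a laboratory-based patient count for them. Separately, the two descriptions of last observation do not agree and carry no on-treatment limit.

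The size cannot be read from the SAP. Under the assumed onset rates and persistence, the missed share of ever-low patients at Week 16 lies between 0% (lows always persist) and about 75% (no persistence). The middle of the range should not be taken as an estimate. The conclusion rests on reading sections 7.2.7 and 7.3 to 7.3.2 together, not on these figures. It concerns the completeness of safety reporting and is worth correcting because the correction is cheap.

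**What to change.** In section 7.3.2, pre-specify a shift table of baseline category against worst post-baseline on-treatment category for the haematology parameters in section 7.2.7: lowest for haemoglobin, white cells, neutrophils and lymphocytes; lowest and highest, separately, for platelets. Base the main version on scheduled visits so that sampling is the same in every arm, and add a supporting version that includes unscheduled on-treatment samples. Present it beside the TEAE-based table of section 7.2.7. While the parameter list is being settled, correct that section's gloss of thrombocytopenia as a fall in red cells.

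Define last observation once, in the same words in sections 7.3 and 7.3.2. State whether unscheduled samples qualify, and set an explicit on-treatment limit. Keep the Week 16 and last-observation tables. Lipids need no change.

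The cost is SAP wording and one more table (with its supporting version), with no new data. Worst-value counts are higher in every arm because they take an extreme over several samples, and the supporting version also depends on how often a patient was sampled. Both must therefore be read against placebo.

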#### ***7.2.6 TEAE by Maximal Severity***

Every AE will be graded by the investigator as mild, moderate, or severe, so for each patient the greatest severity observed can be obtained by comparing the severity of all of a patient's TEAE that share the same SOC or PT. A table of TEAE by maximal severity will be prepared for each treatment arm by SOC and PT.

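### Haematology results of special interest are counted from measured values only as a low/normal/high shift to Week 16 and last observation, so mid-study abnormalities that recover, and the depth of any abnormality, are not counted per arm

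*SAP*

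**What the plan says.** Section 7.2.7 sets the scope: "Adverse events or laboratory results of special interest include infections; myelosuppressive events of anaemia (haemoglobin decreased), leukopenia (white blood cell count decreased), neutropenia", continuing to lymphocytes, thrombocytopenia, raised platelets, lipids, cholesterol and liver tests. (The gloss beside thrombocytopenia refers to red cells; I read it as a slip and take platelets as meant.) Cases are then identified by the preferred term of a treatment-emergent adverse event (TEAE) or by the infections organ class, not by laboratory value.

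The sampling in section 7.3 is "Blood samples for hematology and serum chemistry and urine samples for urinalysis will be collected at baseline and Weeks 4, 8, 12, and 16". For lipids it is "Blood samples for fasting lipid profiles will be collected at baseline and Week 16 post-randomization". On extra draws the rule is "The unscheduled assessments will only appear in data listings", except that one may serve as the last value when Week 16 is missing.

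For values, section 7.3.1 gives descriptive statistics by visit and arm, which under section 2.8 include minimum and maximum. Section 7.3.2 gives the shift: "The grading of each laboratory parameter as low, normal or high will be compared from baseline to Week 16 and to the last observation". Other visits are optional: "Shift tables comparing baseline to the other time points in the study may be generated if warranted after data review".

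Liver tests are treated differently in the same section: "For each of the transaminases the number of patients with any post-baseline elevation exceeding 3 times the upper limit of the normal range" is counted by arm within baseline subsets, and again at 5 and 10 times the limit. Bilirubin and alkaline phosphatase get similar counts. Section 7.4 gives threshold and change counts for vital signs at each visit.

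**The concern.** Section 7.2.7 puts haematology and liver results in the same special-interest list, but only the liver results get patient counts by size of abnormality at any time after baseline. For haematology, measured values collected at Weeks 4, 8 and 12 enter no committed patient count, unless one of them happens to be a patient's last observation.

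A safety reader comparing 2 mg, 4 mg and placebo would want to know how many patients in each arm reached a marked cytopenia at any visit. From measured values, the committed tables do not answer that.

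**Working it through.** The plan states no figure to reproduce here, so the main check is to follow individual patients through the committed outputs.

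| Patient (haematology) | 7.3.2 shift | 7.3.1 by-visit statistics | TEAE tables |
|---|---|---|---|
| Normal at baseline, low at Week 8, normal at Week 16 | normal to normal | visible only if it is that arm's minimum at Week 8; no count | only if reported |
| Normal at baseline, slightly low at Week 16 | normal to low | no count | only if reported |
| Normal at baseline, profoundly low at Week 16 | normal to low, same cell | minimum shows one value; no count | only if reported |
| Low at baseline, lower at Week 16 | low to low | minimum or change may show it; no count | only if reported as worsening |
| Stops early while low, no later value | low at last observation | counted within n at that visit only | only if reported |

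The first three rows are the point. The fourth is the within-class case. The fifth is handled adequately, apart from depth.

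For lipids, the only scheduled post-baseline draw is Week 16, apart from an early-termination sample. The first row therefore hardly arises and only depth remains.

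To give a sense of size I used an illustration. Only arm size comes from the SAP: 120 × 3/10 = 36 per active arm (section 1.3). The rest is assumed:
- Values are normal with SD 1, oriented so that higher is worse, with correlation r = 0.70 or 0.85 between any two visits.
- The proportion p outside the limit u at baseline is 2.5%, 10% or 25%.
- The drug shift d is 0, 0.5 or 1 SD.
- Marked means at least 1 SD beyond the limit. This is a stand-in, not a toxicity grade.

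**Depth.** Marked share of patients abnormal at Week 16 = P(Z > u + 1 − d) / P(Z > u − d). For p = 10%, u = 1.282; with d = 0.5 this is P(Z > 1.782)/P(Z > 0.782) = 0.037/0.217 = 0.17.

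| d | p = 2.5% | p = 10% | p = 25% |
|---|---|---|---|
| 0 | 6% | 11% | 19% |
| 0.5 | 10% | 17% | 28% |
| 1 | 15% | 26% | 40% |

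**Timing (haematology).** I simulated 2,000,000 patients per correlation, with value = √r·b + √(1−r)·e + d at Weeks 4, 8, 12 and 16. The measure is the share of patients marked at any visit who are inside the limit at Week 16, across all p and r:

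| Scenario | Share | Patients per 36 |
|---|---|---|
| No shift | 4–30% | 0.01–0.7 |
| 0.5 SD at all four visits | 3–24% | 0.04–1.1 |
| 0.5 SD at Weeks 4–12, zero at Week 16 | about 17–55% | 0.16–2.7 |

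**Within-class worsening.** Patients abnormal at baseline and worse by at least 1 SD at Week 16: at most about 0.3 per 36 when p ≤ 10% and d ≤ 0.5. At p = 2.5% and d = 0 it is below 0.01. It exceeds 1 only with p = 25%, or with d = 1 and p = 10%; the maximum in the grid is 3.2.

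**The case against.** The best case against is that nothing here is wrong. Section 7.3.2 states a clear rule and contradicts nothing. Three-class shifts with by-visit descriptives are a conventional plan for a Phase 2 trial of this size, and giving liver tests thresholds may be deliberate emphasis. Coverage elsewhere is real. Special-interest TEAE tables count patients per arm, as does the severity table: "A table of TEAE by maximal severity will be prepared for each treatment arm by SOC and PT". TEAEs include worsening from baseline. Minimum and maximum by visit would expose an extreme nadir. Section 1.1 allows further supportive analyses without amendment, and the values remain in the database. The illustration is assumption almost throughout, and its largest timing figures need full recovery on continued treatment, which no section suggests.

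Much of this stands. It settles that the point is an improvement and that the numbers are not forecasts. The missed share is higher with no drug effect than with a constant shift, so in those scenarios it is mostly visit-to-visit noise.

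Two things remain. The TEAE tables depend on the investigator reporting and grading an event, and a minimum is one value, not a count. Shifts at other visits are decided only after data review and would use the same three classes.

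A further fair objection is that worst-value counts grow with the number of draws, so an arm retested more often can look worse. The fix has to deal with that.

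**Conclusion.** The point holds as an optional, low-cost improvement to the safety tables. For haemoglobin, white cells, neutrophils, lymphocytes and platelets, the committed value-based counts miss abnormalities at Weeks 4, 8 or 12 that recover by Week 16, and they do not distinguish depth. This follows from the table design and needs no assumptions. How many patients are affected cannot be derived from the SAP; the illustration suggests anything from almost none to two or three per active arm.

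Three stronger readings are tempting but unsupported:
- A reader might infer that cytopenias go uncounted altogether. They do not: reported events are counted per arm.
- A reader might infer that lipids share the timing gap. With one scheduled post-baseline draw they do not; only depth is at issue.
- A reader might take worsening within an already abnormal class as a major loss. Unless baseline abnormality is common or the drug shift large, it is a fraction of a patient per arm and a minor point.

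**What to change.** In section 7.3.2:

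- Add one table by arm of baseline grade against worst post-baseline grade for haemoglobin, white cells, neutrophils, lymphocytes and platelets. Use CTCAE grades, with fixed ULN multiples for raised platelets. Fix the version and cut-offs before the unblinded review described in section 2.1.
- Report the number and percentage of patients who worsen by at least one grade and by at least two grades.
- Base the main count on scheduled visits. Give a second count that adds unscheduled values, stated as an exception to the section 7.3 rule, so that the effect of extra retesting can be seen.
- For lipids and cholesterol, add only a graded shift from baseline to Week 16 and last observation.
- Keep the low/normal/high shift.

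The cost is SAP wording and one or two table shells, using values already collected. The tables will be sparse, and the grading must be settled in advance.
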